Association between the Irrigation-Agitation Techniques and Periapical Healing of Large Periapical Lesions: A Randomized Controlled Trial

Clinical Trial Number: NCT06204887

Date: 16.05.2024

STUDY PROTOCOL

Local ethics committee approval was obtained from the Ethical Review Committee of the Research Foundation at the Medical Faculty of Recep Tayyip Erdogan University (No: 2023/35) and the study protocol was registered at ClinicalTrials.gov (NCT06204887).

Sample size calculation

The G Power 3.0.10 (University Kiel, Germany) program was used to calculate the effect size. The effect size was calculated based on chi-square analysis data between the control group and the laser group in the Verma, Yadav study [26]. An effect size of 0.51 Cohen d value was found to be sufficient for significance. With a type 1 error of 0.05, it was determined that at least 56 subjects were required for a total of 4 groups, 14 in each study group, with 95% power.

Patient Recruitment and Randomization

Patients were informed about the procedure, and written informed consent was obtained before the commencement of treatment. The study included mandibular single-rooted teeth that were diagnosed with asymptomatic apical periodontitis and had a periapical index (PAI) score of 3 or higher. A total of 97 patients aged 18-65 were evaluated radiographically and clinically for conformity with the inclusion and exclusion criteria. Patients with systemic diseases (diabetes, hypertension, chronic liver disease, coagulation disorders), bone metabolism disease and/or patients using drugs that affect bone metabolism (such as steroids and bisphosphonates) were excluded from the study. Immunosuppressed patients, patients with a history of radiotherapy, pregnant patients, patients with teeth with a mobility of 2 or more (Miller's mobility index), patients with teeth with a periodontal pocket depth of 5 mm or more, patients with generalized asymptomatic apical periodontitis, patients with teeth with internal and external resorption, and patients with teeth with vertical and horizontal root fractures were not included.

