After applying the eligibility criteria, 70 patients were randomly divided into four groups using software (www.random.org) by a blinded researcher who was not otherwise involved in the study according to a standardized procedure. The numbers were placed in dark envelopes and concealed. The envelopes were only opened when the irrigation solution was to be activated. The patients were informed about the study without specifying the group to which they were assigned. All procedures were performed by a single operator with five years of experience ([name]).

CBCT imaging (Planmeca Romexis, Helsinki, Finland) was requested for patients who met the study criteria before the procedure to obtain information about periapical lesion size, proximity to anatomical landmarks, and anatomical variations of the tooth. CBCT images were acquired with a field of view (FOV) of 5×5 cm using ENDO mode, an 85 µm voxel size, 6.3 mA, 90 kV, and 8.7 s.

Clinical procedures

A CONSORT flow diagram outlining the treatment methodology is presented in Figure 1. After the administration of local anesthesia and the placement of a rubber dam, the access cavity was opened with a sterile diamond round bur under water cooling. Each canal was rinsed with 2 mL of sodium hypochlorite and explored with a size 08 K-file (FKG Dentaire, La Chaux-de-Fonds, Switzerland). The working length was determined using an electronic apex locator, Root ZX mini (J. Morita Co., Tokyo, Japan), to be 0.5 mm shorter than a 0.0 reading. The length was confirmed radiographically. After that, progressively larger K-files were passively introduced into the canal until the operator felt the first one to bind at the WL and the next larger one not to reach that position [27]. The first instrument used to bind the canal was recorded for each canal. The crown-down technique was applied with ProTaper Next rotary files (Dentsply Maillefer, Ballaigues, Switzerland) using a torque-controlled endodontic motor (SybronEndo, Glendora, CA, USA) at 300 rpm/2-5.2 Ncm rotation mode according to the manufacturer's instructions. The final instrumentation file was set to 3 sizes larger than the first file used[28]. Between each instrument change, the root canal was irrigated with 5 mL of 2.5% NaOCl (Microvem AF, Istanbul, Turkey) for 1 min. After canal preparation was completed, the final irrigation procedure was carried out with the corresponding irrigation method in each group.

[figure not shown]

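### No blocking or stratification is described and the between-arm volume comparison has no baseline term, so chance imbalance in lesion severity is handled in neither design nor analysis

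*Protocol*

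**What the plan says.** On entry, the protocol (Patient Recruitment and Randomization) takes mandibular single-rooted teeth that "had a periapical index (PAI) score of 3 or higher". This is its only lesion-severity criterion. The title refers to large lesions, but no size threshold is given.

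On numbers, the Sample size calculation concludes that "at least 56 subjects were required for a total of 4 groups, 14 in each study group".

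On allocation, the protocol states that "70 patients were randomly divided into four groups using software (www.random.org) by a blinded researcher who was not otherwise involved in the study". The sentence goes on to mention a standardized procedure without describing it. The next step is that "The numbers were placed in dark envelopes and concealed"; envelopes are opened only when the irrigant is to be activated. Neither document gives a block size, stratification factor, ratio or target arm size.

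On baseline data, PAI is known at screening, and a CBCT scan is taken before the procedure, partly to record lesion size. The protocol (Healing evaluation) says that each patient's volume is compared with the preoperative measurement and that changes are measured.

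On analysis, the SAP compares volumes between groups at each measurement time by ANOVA or Kruskal–Wallis with Bonferroni correction. It tests within-group change by the Wilcoxon signed-rank test, and it examines sex and age. No between-arm analysis includes baseline volume or PAI, and none is specified for change in volume.

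**The concern.** A tooth that starts with a larger lesion can be expected to have more residual volume at 12 months, whatever irrigation technique was used. In a small four-arm trial, chance alone can put noticeably more severe teeth in one arm than in another. Stratifying the allocation would limit this, and adjusting the analysis for baseline would correct for it. The documents describe neither.

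If one arm happens to receive more severe teeth, the unadjusted comparison of 12-month volumes mixes that head start with the effect of technique, and a reader cannot separate them. Even without a visible imbalance, variation in starting volume stays in the error term and makes the test less sensitive than the collected data allow.

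**Working it through.** **Inputs from the documents:** 70 patients; four arms; minimum 14 per arm; PAI 3 or higher; unadjusted between-arm tests. **Assumptions:** the share of teeth at PAI 4–5 (30% to 50%) and the correlation ρ between baseline and 12-month volume (0.3 to 0.7). The documents give neither.

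**1. The plan's figure.** 4 × 14 = 56, so the total and the per-arm minimum agree, and 70 / 4 = 17.5 leaves 3.5 per arm on average. The 95% power does not follow from the inputs as labelled, but that is a separate matter and nothing below depends on it.

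**2. Severity imbalance with near-equal arms.** This is the reading most favourable to the plan: arms of 17, 17, 18 and 18. With K high-PAI teeth among 70, the chance that the arms receive a, b, c and d of them (a + b + c + d = K) is

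C(17,a) · C(17,b) · C(18,c) · C(18,d) / C(70,K).

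Summing over all outcomes where the highest and lowest arm proportions differ by at least 0.30:

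- K = 21 (30% high): 0.23
- K = 35 (50% high): 0.31

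For a gap of at least 0.20, simulation gives 57% and 60%. These figures concern the most extreme of six pairs of arms. For one pair fixed in advance, the chance of a 30-point gap is about 6% to 9%.

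**3. A continuous baseline measure, such as lesion volume.** With the same arm sizes and a normally distributed measure, the largest standardised difference between any two arms has a median of 0.47 and exceeds 0.5 with probability 45%.

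**4. Consequence for the outcome.** A baseline gap of 0.47 SD carries over to about ρ × 0.47 SD at 12 months: 0.3 × 0.47 = 0.14, 0.5 × 0.47 = 0.24, 0.7 × 0.47 = 0.33. Adjusting for baseline multiplies the residual variance by about 1 − ρ²: 0.91, 0.75 and 0.51 for the same three values.

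**5. Arm sizes, only if allocation was unrestricted.** If each of the 70 is assigned independently with probability 1/4, the exact multinomial probability that at least one arm has fewer than 14 is 0.495. The median gap between the largest and smallest arm is 8. If a list was split equally, the smallest arm is 17 and this probability is 0.

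**6. Effect of stratified blocks.** Take mixed blocks of 4 and 8 within two strata (PAI 3; PAI 4–5). An unfinished block leaves arms at most 2 apart in a stratum, so at most 4 apart overall. If the smallest arm is m, then m + 3(m + 4) ≥ 70, so m ≥ 14.5 and every arm has at least 15. The high-PAI counts differ by at most 2, which is about 2/17, or 12 percentage points.

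**The case against.** Unstratified randomisation is valid and balances severity in expectation, and stratification is optional. That stands. The size in step 2 also depends on an assumed PAI distribution and on the worst of six pairs. The plan does not ignore baseline either: it compares groups at each measurement time, which would reveal an imbalance, and it measures change within patients. But revealing an imbalance does not correct for it, and the SAP specifies no between-arm test that uses each patient's starting volume.

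Three stronger readings are tempting and not supported.

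- *The trial had an even chance of an arm below 14.* Allocation was "by a blinded researcher who was not otherwise involved in the study according to a standardized procedure", and that procedure may have been an equal split. The flow diagram, not visible here, may show the arm sizes. That 70 is not divisible by 4 is irrelevant, since 17 and 18 both exceed 14. Nor would a shortfall in one arm cost much. Reading 0.51 as the ANOVA effect size f (an assumption), 14 per arm gives 88.4% power, whereas unrestricted allocation of 70 averages about 94%, and 93% to 94% in draws with an arm below 14.
- *Chance imbalance produces false positives above 5%.* The null distribution of the test already allows for chance imbalance.
- *The documents rule out blocking or stratification.* They are silent on it.

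**Conclusion.** The concern holds in a limited form. No control of severity is described at allocation, and none is specified in the between-arm analysis. With near-equal arms, a gap of 30 points or more in high-PAI share between the extreme arms arises in about 23% to 31% of randomisations, if 30% to 50% of teeth are PAI 4–5. The cost is lost precision and a harder reading of any difference found. It is not an invalid randomisation or an inflated type 1 error.

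The roughly 50% chance of an arm below 14 is conditional on unrestricted allocation and should not be quoted without that condition. The analysis gap is the firmer half of the point: it can be read directly from the SAP and does not depend on how the list was made.

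**What to change.** **(a) In the SAP.** Make the between-arm comparison of 12-month lesion volume a baseline-adjusted model: ANCOVA with pre-procedure CBCT lesion volume as covariate, or at least PAI stratum. Use log or rank-transformed volume if the residuals are not normal. If any lesion resolves to zero volume, the log needs a stated offset, whereas ranks do not. Baseline volume is preferable to PAI because it is on the outcome's own scale. This replaces the one-way ANOVA or Kruskal–Wallis for that comparison, so it is a change of model and slightly more complex, but it uses only data already collected. If results are already known, report it as an added analysis.

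**(b) In the protocol.** State how the list was made and the intended arm sizes. The text is in the past tense, so the 70 may already be allocated. If allocation is not complete, have the uninvolved researcher prepare envelopes as permuted blocks of mixed size 4 and 8, in separate sets for PAI 3 and PAI 4–5, and include the stratum in the model. This costs a second envelope set and no extra patients or measurements. The downside is that the single operator could sometimes guess the next assignment. Mixed block sizes, and opening envelopes only at activation, limit this.

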Association between the Irrigation-Agitation Techniques and Periapical Healing of Large Periapical Lesions: A Randomized Controlled Trial

Clinical Trial Number: NCT06204887

Date: 16.05.2024

Statistical analysis

Analyses were carried out in the IBM SPSS 25 program. As the first step of the statistical analysis, the normality of the data was checked with the Shapiro–Wilk test. When normality was ensured, the Wilcoxon signed rank test was applied to examine the difference between the means of two dependent groups. ANOVA was used to examine the difference between the means of three or more independent groups. In cases where the data were not normally distributed, the Kruskal–Wallis test was performed. The post hoc Bonferroni correction was used to determine the group or groups that were significantly different.

Pearson's chi-square test was applied to examine the relationships between study groups and sex. The Kruskal–Wallis test was applied to examine the differences between the average ages of the participants in the study groups. Spearman correlations were used to control for the relationships between age and lesion volume measurements obtained at different times and from different study groups. To compare lesion volume measurements according to study group at different measurement times, ANOVA and the Kruskal–Wallis test were applied. Bonferroni correction were performed to compare the groups. Wilcoxon signed rank tests were used to compare lesion volume measurements according to different measurement times in the study groups.

For comparisons of lesion volume measurements at different measurement times in the study groups, assumptions were checked, and Wilcoxon signed-rank tests were used. Analyses were performed with the IBM SPSS 25 (SPSS Inc., Chicago, IL) program. The Pearson chi-square test was used to examine the relationships between study groups and sex. The Spearman correlation test was used to assess the relationships between lesion volume measurements obtained at different times and study group and age.

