The preoperative and 1-year postoperative CBCT images of the patients were measured following the same steps in the ITK-SNAP program. We used the same techniques used by Schloss et al[15]. First, the captured CBCT images were exported in DICOM file format from the Planmeca Romexis software. The exported images were then opened with ITK-SNAP software. Using the highest resolution allowed by the captured CBCT images (0.09 mm), the slice thickness and slice interval were set to 0.09 mm. The ITK-SNAP program includes a semiautomatic segmentation feature, which was utilized. In this feature, automated spherical fillers, or bubbles, as referred to in the program, were placed according to the grayscale of the lesion. Repeated runs were performed until the entire area of the lesion was filled, with the bubbles placed in the lesion area. After the internal area of the lesion was completely filled, the images were evaluated from axial, sagittal, and coronal sections to correct any possible overfilling or underfilling situations due to artifacts from canal filling materials using a manual marker. The volume of the painted area obtained was calculated in mm³ using the program's feature. The evaluation of the tomography images obtained before and after treatment was conducted at one-month intervals. The images were provided to the evaluators in a randomized manner.

The volume data were compared with the preoperative CBCT measurements for each patient. The volume changes were measured, and the long-term outcomes of the procedures were compared.

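### Does tying the Wilcoxon signed-rank test to normality in one SAP paragraph, and not in the next two, leave the pre-post analysis undefined?

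*SAP*

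**What the plan says.** The SAP has one section, Statistical analysis, in three paragraphs.

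- **Paragraph 1** sets general rules. It opens with a check: "the normality of the data was checked with the Shapiro–Wilk test". Then: "When normality was ensured, the Wilcoxon signed rank test was applied to examine the difference between the means of two dependent groups". After assigning ANOVA to three or more independent groups, it adds: "In cases where the data were not normally distributed, the Kruskal–Wallis test was performed".
- **Paragraph 2** turns to the trial's own variables: "Wilcoxon signed rank tests were used to compare lesion volume measurements according to different measurement times in the study groups".
- **Paragraph 3** repeats the assignment: "For comparisons of lesion volume measurements at different measurement times in the study groups, assumptions were checked, and Wilcoxon signed-rank tests were used".

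The Protocol, under Healing evaluation: lesion area and volume calculation, fixes the two measurement times: "The preoperative and 1-year postoperative CBCT images of the patients were measured following the same steps in the ITK-SNAP program". Each patient therefore supplies one pair of volumes.

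**The concern.** Paragraph 1 seems to have the logic backwards. The signed-rank test is usually chosen when normality is in doubt; here it is tied to normality being met and described as comparing means. The only fallback that paragraph 1 gives for non-normal data is Kruskal–Wallis, which compares independent groups and cannot handle paired volumes. Read alone, the paragraph leaves non-normal pre-post volumes without a test. Paragraphs 2 and 3 carry no such condition, and paragraph 3 mentions a check of assumptions without naming them or saying what the result decides.

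If this were a real gap, two analysts could choose different paired tests for the same data, or the choice could be made after seeing the results. A signed-rank p-value might also be reported as evidence about a mean change.

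**Working it through.** The SAP gives no figure on this point, so there is none to reproduce. The check is to set the paragraphs side by side, then to bound what a different reading could change.

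**Step 1. Which paired test does each paragraph give?**

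| Result of normality check | Paragraph 1 | Paragraph 2 | Paragraph 3 |
|---|---|---|---|
| Normal | Wilcoxon signed-rank | Wilcoxon signed-rank | Wilcoxon signed-rank |
| Not normal | no paired test named | Wilcoxon signed-rank | Wilcoxon signed-rank |

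Wherever a paired test is named, it is the same one. The single empty cell is filled by two paragraphs that address lesion volume directly. Paragraph 1 is generic; paragraphs 2 and 3 are specific, and the specific statements govern. No cell contains a paired t-test.

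**Step 2. Is the named test sound in both rows?** Yes. Under normality it is valid, and its asymptotic efficiency relative to the t-test is 3/π = 0.955. Without normality it remains valid for its own null hypothesis, that the paired differences are symmetric about zero.

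**Step 3. How many tests are involved?** One pre-post comparison in each of four groups gives four tests. The between-group comparisons use ANOVA or Kruskal–Wallis and do not depend on this sentence.

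**Step 4. Background: what if a paired t-test had been meant for normal differences?**

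Inputs:
- n = 14 per group, the planned minimum (56/4; Protocol, Sample size calculation).
- n = 17 or 18 per group, from "70 patients were randomly divided into four groups" (Protocol, Patient Recruitment and Randomization): 70/4 = 17.5, assuming a near-equal split.
- Two-sided alpha 0.05.
- Standardised changes of 0.6, 0.8 and 1.0. These are assumed, since the documents give none.

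Simulation used 200,000 samples per cell with normal paired differences (Monte Carlo standard error at most 0.0011). The t-test values agree within 0.001 with the noncentral-t formula, whose noncentrality is the standardised change × √n; for example 0.8 × √14 = 2.99 on 13 degrees of freedom.

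| n | Change | Paired t | Exact Wilcoxon | Difference (points) |
|---|---|---|---|---|
| 14 | 0.6 | 0.547 | 0.530 | 1.7 |
| 14 | 0.8 | 0.790 | 0.772 | 1.8 |
| 14 | 1.0 | 0.932 | 0.922 | 1.0 |
| 17 | 0.6 | 0.641 | 0.604 | 3.7 |
| 17 | 0.8 | 0.872 | 0.845 | 2.7 |
| 17 | 1.0 | 0.972 | 0.962 | 1.0 |
| 18 | 0.6 | 0.670 | 0.647 | 2.3 |
| 18 | 0.8 | 0.892 | 0.876 | 1.6 |
| 18 | 1.0 | 0.979 | 0.973 | 0.6 |

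At n = 17 the asymptotic Wilcoxon p-value gives power 0.627, 0.859 and 0.966, so the differences shrink to 1.4, 1.3 and 0.6 points. At n = 14 and 18 the asymptotic and exact versions agree.

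Type I error, t / exact Wilcoxon, is 0.050/0.050 at n = 14, 0.051/0.045 at n = 17 (asymptotic 0.051) and 0.050/0.048 at n = 18.

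These figures do not measure harm from the wording. The t-test is not in the SAP, so the small power difference is the same whether or not the sentence is tidied. They show only that the other reading would also be harmless.

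**The case for a change.** The strongest case for acting is that an SAP should let a second analyst choose the test without weighing one paragraph against another, and that the repair costs only two or three phrases. The authors may also have intended a branch: paragraph 1 starts from a normality check and speaks of means, which suits a paired t-test for normal differences and Wilcoxon otherwise. On that view the later paragraphs do not fully settle the intent.

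What stands is that the sentence is badly worded and that calling the test a comparison of means is loose, although under symmetric differences it does bear on the mean. What does not stand is that the analyst is left guessing. Lesion volume is the only paired comparison to which the SAP assigns a test, and it is assigned twice, by name, without a branch. A supposed t-test branch has no text behind it.

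Nor should the phrase "assumptions were checked, and Wilcoxon signed-rank tests were used" simply be struck out. Symmetry of the paired differences is a legitimate assumption to check when the test is read as one of location, so deletion could remove a sensible step.

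**Conclusion.** The concern does not call for a change. It is a clerical slip with no gain from correction: following the plan as written leads to a Wilcoxon signed-rank test in each of the four groups, which is valid whether or not the volumes look normal. Correcting the wording would change no planned test, no error rate, no power and no sample size, and the randomised comparison is outside its reach.

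This rests on giving the paragraphs about lesion volume precedence over the general sentence, which is the ordinary way to read such a plan. If that reading were wrong and a paired t-test had been meant for normal differences, the power difference would be 0.6 to 3.7 points under the assumed changes, normal differences and near-equal group sizes. That is too small to matter for a secondary, within-group description.

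### Holm's step-down procedure would be a cheap and slightly more powerful replacement for plain Bonferroni when the four groups are compared pairwise

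*SAP*

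**What the plan says.** The SAP's Statistical analysis section starts the between-group comparison with an omnibus test: "To compare lesion volume measurements according to study group at different measurement times, ANOVA and the Kruskal–Wallis test were applied". The pairwise step follows: "The post hoc Bonferroni correction was used to determine the group or groups that were significantly different". The same section later repeats it: "Bonferroni correction were performed to compare the groups". It names no step-down or other sequential version, does not state the number of comparisons, and does not confine them to active arm versus control. It describes tests and correlations only; no confidence intervals are planned, simultaneous or otherwise.

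The Protocol, under Patient Recruitment and Randomization, states that "70 patients were randomly divided into four groups using software". Under Sample size calculation it sets the level ("With a type 1 error of 0.05") and the size: "at least 56 subjects were required for a total of 4 groups, 14 in each study group, with 95% power". The effect size is described thus: "An effect size of 0.51 Cohen d value was found to be sufficient for significance". Its basis is also given: "The effect size was calculated based on chi-square analysis data between the control group and the laser group". Neither document gives a mean or SD for lesion volume.

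**The concern.** A significant omnibus test says only that the four techniques are not all alike. The pairwise step says which ones differ, and that is what a reader of the trial will want to know.

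Single-step Bonferroni holds all six pairs to 0.0083, even after some pairs have already been declared different. Holm relaxes the threshold as pairs are declared, at the same family-wise level and under the same conditions. The usual reason to stay with Bonferroni is that it yields matching simultaneous confidence intervals, and this SAP plans none. What is at stake is some power to complete the picture of which techniques differ, in arms planned at 14. The validity of the analysis is not at stake.

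**Working it through.** **Inputs.** Four groups, alpha 0.05, 14 per arm and effect size 0.51 come from the Protocol. Bonferroni after ANOVA or Kruskal–Wallis comes from the SAP. Assumed here: two-sided tests, equal arms, SD = 1.

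**The plan's own figure.** The stated inputs do not lead directly to 56:
- 0.51 as Cohen d, 95% power: n per arm = 2(1.960 + 1.645)²/0.51² = 99.9, so 100.
- 0.51 as chi-square w: total 50, 60 or 67 for 1, 2 or 3 degrees of freedom.
- 0.51 as f in a one-way ANOVA: total 72; power at 56 is 88.4%.
- 0.51 as f for the between-group factor of a repeated-measures ANOVA, two measurements, correlation 0.5: exactly 56 (95.9%; 52 gives 94.3%). The range is 48 to 64 for correlations 0.3 to 0.7. The documents state neither this test nor a correlation.

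The role of 0.51 is therefore open, and both the d and the f reading are carried forward.

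**Thresholds.** Pairs: 4 × 3/2 = 6. Bonferroni uses 0.00833 for all six. Holm compares the sorted p-values with 0.00833, 0.0100, 0.0125, 0.0167, 0.025 and 0.05, stopping at the first failure.

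**Why Holm loses nothing.** No Holm threshold is below 0.05/6, so every p-value that passes Bonferroni passes Holm. The first threshold is the same, so the chance of at least one rejection is identical.

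**Why Holm keeps 5%.** Suppose m of the six nulls are true. Before the first false rejection at most 6 − m pairs have been rejected, so the threshold at that step is at most 0.05/m. The family-wise error is then at most m × 0.05/m = 0.05, whatever the dependence. Bonferroni's bound is m × 0.05/6: 2.5% when one arm differs from three equal arms (m = 3) and 1.7% for two against two (m = 2). Holm spends part of what Bonferroni leaves unused.

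**Effect patterns.** With f = SD of the group means/SD within groups = 0.51:
- One arm against three: difference × √3/4 = 0.51, so 1.18 SD.
- Two against two: difference/2 = 0.51, so 1.02 SD.
- Evenly spaced: step × √5/2 = 0.51, so steps of 0.456 SD and a range of 1.37 SD.

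Under the d reading the largest difference is 0.51 SD.

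**Simulated power, 14 per arm** (F-test at 0.05, then pooled-SD t contrasts; 40,000 trials per pattern, standard error at most √(0.25/40,000) = 0.25 points; Bonferroni → Holm):

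| Pattern | Average per true contrast | All true contrasts found | At least one found |
|---|---|---|---|
| Two v two, f = 0.51 | 48.8% → 53.4% | 17.0% → 25.6% | 80.6% for both |
| One v three, f = 0.51 | 64.5% → 67.5% | 41.4% → 47.8% | 85.5% for both |
| Evenly spaced, f = 0.51 | 29.4% → 32.2% | not tabulated | 84.7% for both |
| One v three, d = 0.51 | 8.8% → 9.3% | not tabulated | see below |
| Two v two, d = 0.51 | 8.9% → 9.6% | not tabulated | not tabulated |

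Without the F-test gate, two v two at f = 0.51 gives 48.7% → 53.4%, with all four found 16.8% → 25.4%. One v three at d = 0.51 gives 9.1% → 9.6%, with 20.5% for at least one under both methods. It does not matter whether the control or another arm is the one that differs; that is a single pattern.

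**Kruskal–Wallis branch** (Dunn contrasts after a significant omnibus test, 14 per arm, f = 0.51): two v two 40.6% → 45.0%, all four 8.7% → 15.8%; one v three 54.7% → 58.2%, all three 25.7% → 32.7%. At least one is unchanged at 77.1% and 82.0%.

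**At 17 per arm** (70/4 = 17.5), f = 0.51: two v two 60.0% → 65.2%; one v three 75.9% → 78.7%. Baseline power is higher and the gain similar.

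**False rejections, 14 per arm.** With no true differences, 3.7% for both. With one arm differing (f = 0.51), 2.3% → 3.5%. In that pattern about 10.2% of trials gain some extra rejection and 1.5% gain a false one.

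**The case against.** The strongest reply is that nothing is wrong. Bonferroni controls the error rate, suits the purpose the SAP gives it, and contradicts no other statement. That stands, and it limits this point to an efficiency suggestion.

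The benefit is also narrow. A reader might infer that Holm would make the trial more likely to find a difference between techniques. It would not, because the first threshold is 0.05/6 under both methods. Under the protocol's own label for 0.51 the gain is under 1 point, and the documents give no grounds for preferring the larger figure.

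Nor is the change free of drawbacks. False rejections increase, though within 5%. Simultaneous intervals, if added later, would be simpler to match to Bonferroni. Both documents describe the work in the past tense, including the 12-month imaging and the analyses. They do not say whether group results were known when the plan was fixed. If they were, moving to a more permissive adjustment would be a post hoc choice.

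Finally, the family is inferred. The SAP does not define it, and it applies the group comparisons at more than one measurement time. Holm within each time leaves error across times where Bonferroni within each time leaves it. What survives is the dominance: on the same six p-values Holm never declares fewer differences and keeps the same error bound.

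**Conclusion.** The point holds as a low-cost improvement. That Holm rejects at least as much at the same 5% family-wise level is a mathematical result and needs no assumption about effects, distribution or sample size, provided each pairwise test is itself valid. That it complicates nothing else rests on the SAP's silence about intervals.

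The size of the gain does rest on assumptions. At 14 per arm, average power per true contrast rises by under 1 point if 0.51 is the largest standardised difference. If 0.51 acts as f, it rises by about 3 to 5 points, and the chance of finding every true contrast goes from 17% to about 25% (two v two) or from 41% to 48% (one v three).

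Two stronger readings are not supported. One is that Bonferroni makes the comparison invalid: it exceeds no error rate. The other is that the plan demonstrably forfeits several points of power: without lesion-volume means or SDs, the documents cannot separate a gain of 5 points from one below 1.

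**What to change.** In the SAP's Statistical analysis section, replace both mentions of the Bonferroni correction with: *Holm step-down adjustment of the six pairwise p-values at each measurement time*. Apply it to both the ANOVA and the Kruskal–Wallis branch. Add the rule: sort the six unadjusted p-values, compare them in order with 0.05/6, 0.05/5, 0.05/4, 0.05/3, 0.05/2 and 0.05/1, and stop at the first failure. This also states the number of comparisons and the family, which the SAP now leaves to inference.

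The cost is one sentence and the sorting of six p-values. The six comparisons and the 5% level stay as they are, with false rejections slightly more frequent inside that limit. If group results were already known, label the change post hoc or report Holm beside Bonferroni. If simultaneous intervals are wanted later, settle how they will be matched to the tests at the same time.
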